### 20.3 Description of Statistical Methods

### 20.3.1 General Approach

We recognize that the relatively small sample sizes proposed in the RCT are not likely to produce statistical significance, unless the effect sizes are remarkably high. We will carry out a full Mixed Model Repeated Measures (MMRM) statistical analysis in case CBD does perform so well. However, the main focus of the statistical analysis of the results of the trial will be to characterize the effect sizes and response rates across the various measurement domains and the profiles of individuals who are treatment successes. The intent to treat (ITT) population will contain all randomized patients who receive at least one dose of double-blind study medication and from whom at least one post-baseline (B1) efficacy measurement is obtained while on study medication. The efficacy analysis will be based on the ITT population. Two-sided hypothesis testing will be utilized. Tests with p-values less than or equal to 0.05 will be considered statistically significant, while those less than equal to 0.10 will be considered suggestive. Since this trial is the first use of this treatment for this diagnostic indication, no adjustments of p-values for multiple comparisons will be made. Thus, all control of type 1 error is contrast-wise. All confidence intervals will be two-sided with 95% confidence. Mean treatment effect, standard errors, and 95% confidence intervals will be derived from fully adjusted models on outcomes averaged across the treatment period. Cohen's d and p-values will be calculated from fully adjusted models with appropriately transformed outcome variables. For dichotomous drinking outcomes, prevalence rates will be calculated. Odds ratios (ORs) and p-values will be derived from logistic regression models including treatment group.

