### 20.3.2 Analysis of the Primary Endpoint(s)

For Hypothesis 1a, Safety and tolerability, the frequency of adverse events will be analyzed for the entire sample at all time points, tabulated for each treatment group, and compared using chi-squared tests. The safety analysis will be largely descriptive of outcomes for the entire study population. The incidence of AEs will be summarized by system organ class, preferred term, the likelihood of its relationship to the treatment, and severity for each treatment group. Clinical laboratory data will be summarized by type of test. Frequency and percentage of patients whose values fall outside of reference ranges will be presented for each measurement.

For Hypothesis 1b, Alcohol Use. The Primary outcome measure, number of drinks per day, will be analyzed with an MMRM to assess differences in change from baseline. The primary contrast is change from baseline (B1) at week 6 (T8). The model at each time point will include terms for treatment, time and treatment by time interaction as factors and the baseline value for each score as a covariate. Parameter estimation will be based on REML and to begin an unstructured covariate matrix will be used. If the model fails to converge, the form of the covariance matrix will be chosen based on Akaike's Information Criteria, and Schwarz' Bayesian Criterion. Model-based LS means will be obtained for change from baseline to each time point for each treatment group. At each time point, contrasts between CBD and placebo will be obtained. Secondary alcohol use measures will be tested with MMRM sequentially in a closed testing union intersection paradigm in the order listed in section C.8.3. Validity of the p-value will extend until the first test fails to have a p-value smaller than a two-sided alpha of 0.05. The analyses will continue for all measures but the resulting p-value will be nominal.

For Hypothesis 2, PTSD symptoms, the primary outcome measure, total score of the PCL-5, will be analyzed in the same way as the primary outcome for alcohol use. The primary contrast is change from baseline (B1) at week 6 (T8).

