#### #S17-00949

scores between Post and Pre. This difference measure of alcohol craving will be calculated at Baseline, and at week 6 of the clinical trial (T8). The outcome analysis will be conducted with an MMRM model that includes fixed effects for treatment C, (CBD vs. placebo) and clinical trial time T, a random effect for subjects, and a treatment by clinical trial time interaction (C\*T). The model will provide least-square mean estimates of difference scores at each session for each treatment. Between treatment outcome contrasts will be performed at Baseline, as a measure of the equivalence of the groups, and at T6 and for the difference between T6 and Baseline. For parameter estimation, the form of the covariance matrix will follow the procedures described for the analysis of Aim 1. Secondary outcome measures will be Negative Emotion, and Psychophysiological arousal. These outcomes will be analyzed in a similar manner to the primary outcome, alcohol craving.

For Hypothesis 3b: Mechanism, AUD and PTSD related measures and cognition (craving, self-efficacy, anxiety, cognitive measures) will be analyzed in the same way as the primary outcome for alcohol use. The primary contrast is change from baseline (B1) at week 6 (T8).

For Hypothesis 3c: Mechanism, anandamide, within- and between-group comparisons of plasma anandamide levels will be assessed following 45 minutes (T1), 1 day (T2), 1 week (T3), 2 weeks (T4), 4 weeks (T6), 6 weeks (T8) of treatment with CBD vs. placebo, and one week (T9) after the completion of treatment. Effects of dose will be assessed and the interaction between group and time- point will be evaluated.

For Hypothesis 4, plasma CBD and THC levels will be analyzed in the same manner as anandamide in Hypothesis 3c.

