## 20.4 Sample Size

We will phone screen approximately 600 participants, and enroll approximately 150 participants to randomize a total of 48 participants (through week 6/T8). In this pilot study sample sizes are obviously quite limited. A simple t test of mean differences requires an effect size of .939 to have .8 power. We have chosen an unbalanced design with more subjects on CBD to maximize the ability to characterize response to treatment for use in planning future confirmatory trials and still have valid hypotheses tests.

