### 20.5 Measures to Minimize Bias

### 20.5.1 Enrollment/Randomization/Masking Procedures

Enrolled participants that pass screening will be randomized using a 5:3 ratio to receive either 600mg CBD/day (PO) or placebo respectively for 6 weeks (N=30 participants on CBD and N=18 participants on placebo). Treatment assignment will be known only to a designated unblinded study staff member in charge of dispensing study medication under direct PI supervision, but the blind can be broken if necessary, e.g., in case of a serious reaction during drug administration.

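### The primary MMRM lists no baseline-by-time term; if the correlation with baseline declines over visits, the shared slope under-corrects the week-6 contrast, modestly unless the decline is strong

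*Combined protocol and SAP*

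**What the plan says.** Section 20.3.2 (Hypothesis 1b) analyses drinks per day as change from baseline in an MMRM fitted by REML, starting from an unstructured covariance. The listed terms are "terms for treatment, time and treatment by time interaction as factors and the baseline value for each score as a covariate". The sentence opens "The model at each time point will include terms for treatment", which is loose. A model that contains time and treatment-by-time is nevertheless one joint model over the visits, not a separate model per visit. The primary contrast is the change from B1 to T8.

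PCL-5 (20.3.2, Hypothesis 2) and the Hypothesis 3b measures (20.3.3) "will be analyzed in the same way as the primary outcome for alcohol use", again with T8 as the primary contrast. No baseline-by-time term appears anywhere. Section 20.5.1 allocates 5:3 ("N=30 participants on CBD and N=18 participants on placebo") and mentions no stratification. Section 20.1 leaves a formal SAP to be written before database lock and unblinding.

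**The concern.** With a single baseline coefficient, the relation of change to baseline is forced to be equal at all visits. If early visits track baseline closely and week 6 does so less, the right slope differs by visit. The fitted common slope is then a weighted average in which early visits, with their smaller residual variance, dominate. Week 6 is the only visit in the primary contrast, and its adjustment would be too weak. If the CBD arm happened to start with heavier drinking, part of its regression to the mean at week 6 would stay in the estimate and favour CBD. With the opposite imbalance it would favour placebo. Section 20.3.1 makes estimation of effect sizes the main aim, and 20.4 intends the results for planning later trials, so the accuracy of this one estimate matters.

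**Working it through.** **The plan's own figure.** The only design calculation (20.4) is "A simple t test of mean differences requires an effect size of .939 to have .8 power". At 30 v 18 and two-sided 0.05, a t test reaches 0.8 power at 0.853; 0.939 reproduces at 25 v 15. That is a separate matter. The figure contains no baseline correlation and neither supports nor weakens this point.

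**Inputs from the documents:** 30 v 18; the model terms above; unstructured covariance; PCL-5 at weeks 2, 4, 6 and 7 (4.2.2, 7.1.7); drinking weekly (4.1). **Assumed, because the documents do not give them:** all correlations, and equal SDs at all visits (units are baseline SDs).

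**Step 1, chance imbalance.** The baseline difference d0 has SD sqrt(1/30 + 1/18) = 0.298. P(|d0| > 0.3) = P(|Z| > 1.006) = 31%.

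**Step 2, slopes.** With baseline correlation r_j at visit j, the slope of change on baseline is b_j = r_j - 1. The shared slope tends to b_c = sum of w_j b_j. The weights w are proportional to S^-1 1 and sum to 1, where S is the visit covariance given baseline.

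Mild example at weeks 2, 4, 6: r = 0.7, 0.6, 0.5; between-visit correlation 0.7 for adjacent visits and 0.6 two apart. S has diagonal 0.51, 0.64, 0.75 and off-diagonals 0.28, 0.25, 0.40. The weights are 0.53, 0.25, 0.22, so b_c = -0.368 against b_6 = -0.500.

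**Step 3, effect at week 6.** With complete data the two models differ at T8 by (b_6 - b_c) x d0. Write g for |b_6 - b_c|. The shift at a 0.3 SD imbalance is 0.3g. The added variance is g^2(1/30 + 1/18), against a contrast variance of (1 - r_6^2)(1/30 + 1/18), so

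SE ratio = sqrt(1 + g^2/(1 - r_6^2)).

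Mild: sqrt(1 + 0.132^2/0.75) = 1.012, and the shift is 0.040 SD.

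| Assumed pattern | b_6 | b_c | g | SE ratio | Shift at 0.3 SD |
|---|---|---|---|---|---|
| Flat 0.6, weeks 2, 4, 6 | -0.400 | -0.400 | 0 | 1.000 | 0 |
| Mild 0.7, 0.6, 0.5, weeks 2, 4, 6 | -0.500 | -0.368 | 0.132 | 1.012 | 0.040 |
| Mild 0.7, 0.6, 0.5, 0.45, weeks 2, 4, 6, 7 | -0.500 | -0.391 | 0.109 | 1.008 | 0.033 |
| Mild 0.70 to 0.50, weekly 1-6 | -0.500 | -0.369 | 0.131 | 1.011 | 0.039 |
| Strong 0.8, 0.6, 0.4, weeks 2, 4, 6 | -0.600 | -0.250 | 0.350 | 1.070 | 0.105 |
| Strong 0.80 to 0.30, weekly 1-6 | -0.700 | -0.266 | 0.434 | 1.099 | 0.130 |

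**Step 4, simulation at 30 v 18 with no drug effect.**
- SE ratios were 0.988-0.996 (flat), 1.006-1.014 (mild) and 1.064-1.104 (the two strong patterns). The error on these ratios is about one percentage point.
- A weekly decline from 0.80 to 0.45 gave 1.042 and a shift of 0.277 x 0.3 = 0.08 SD.
- PCL-5 at weeks 2, 4, 6, 7 with a decline from 0.75 to 0.52 gave 1.006 and 0.142 x 0.3 = 0.04 SD.
- The smallest loss seen under strong decline was about 3%. With r_6 = 0.45 the formula gives g = sqrt((1.03^2 - 1) x 0.7975) = 0.22, a shift of 0.07 SD.
- In the 600-700-trial runs (0% or 15% dropout), average bias of the single-slope model was within 0.02 SD and its type I error was 3.5-5.5%.

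**Step 5, one loss or two?** For the 0.80 to 0.45 pattern the imbalance shift alone predicts sqrt(1 + 0.277^2/0.7975) = 1.047, which accounts for the simulated 1.042. The larger standard error and the leftover imbalance are the same quantity.

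**The case against.** The strongest case against is that nothing in the documents shows a decline. With a flat correlation the planned model is right, and about 1% more precise. Under mild decline the shift of about 0.04 SD is small beside a contrast SE of about 0.26 SD. A common slope is a parsimonious choice at 48 participants, and the SAP is still to be written. All of that stands. It is why the point is conditional and its size modest.

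Section 20.3.1 also reports effects averaged over treatment, where a shared slope matters less. In the mild three-visit example the average slope is -0.400 against -0.368, a gap of 0.032 rather than 0.132. But 20.3.2 names T8 as the primary contrast.

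The weekly grid is uncertain too. Section 4.1 says weekly, while the week 3 and week 5 calls in 7.3.3 list no alcohol-use evaluation. The mild result is nearly the same on the grids tried. The calculations also assume normal outcomes, whereas 20.3.1 plans transformed ones.

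A reader might infer more than the documents support:
- **That CBD's effect will be biased.** The remainder is symmetric over randomisations and averages to about zero.
- **That regression to the mean is left uncorrected.** In the mild case an unadjusted change score leaves 0.500 x 0.298 = 0.149 SD per 1-SE imbalance. The planned model leaves 0.132 x 0.298 = 0.039.
- **That every Hypothesis 3b outcome is affected.** Cognition is measured only at T2 and T8 (4.2.2), or at baseline and the end of treatment (4.1). Either way there is one follow-up, so no interaction with time can exist.

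**Conclusion.** The omission is real and sits in the model for both efficacy primaries. Whether it costs anything depends on how the correlation with baseline changes over six weeks, which the documents do not give. Under the assumed ranges the week-6 standard error is unchanged (flat), about 1% or less larger (mild decline, including the PCL-5 pattern of 0.75 to 0.52), or about 3-10% larger (strong decline). The 10% end, 1.099, is equivalent to losing 48 x (1 - 1/1.099^2), or about 8, of 48 participants. The shift at a 0.3 SD imbalance runs from nothing, through 0.03-0.04 SD, to 0.07-0.13 SD. It is one loss described in two ways and not a threat to the validity of the test. The case for changing the model is that the possible loss exceeds the cost of the extra term. This is a cheap improvement, not a fatal flaw.

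**What to change.** In 20.3.2, and in the SAP to be written, list the fixed effects as treatment, time, treatment-by-time, baseline and baseline-by-time. Apply this to drinks per day, PCL-5 and those Hypothesis 3b outcomes that have a pre-dose baseline and at least two later visits (craving, self-efficacy, anxiety and mood by the schedules in 4.2.2 and 7.1.6), but not to cognition. Keep the T8 LS-mean contrast as primary. If the sponsor prefers a common slope, the SAP should justify it before unblinding.

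The cost is one parameter per visit beyond the first: two for PCL-5 at weeks 2, 4 and 6 (three with week 7), and five for drinks per day on a weekly grid. The standard error is up to about 1% larger if the baseline correlation does not decline. No new data are needed.

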### 20.3.3 Analysis of the Secondary Endpoint(s)

For hypothesis 3a: Mechanism, traumatic stress-induced craving: The primary outcome measure will be alcohol craving. Alcohol craving outcomes within a session will be examined in terms of a created measure of a difference of difference scores: first, the difference score of the alcohol craving response to trauma and to neutral challenges calculated for the Pre and for the Post session time points, and second, the difference of the

#### #S17-00949

scores between Post and Pre. This difference measure of alcohol craving will be calculated at Baseline, and at week 6 of the clinical trial (T8). The outcome analysis will be conducted with an MMRM model that includes fixed effects for treatment C, (CBD vs. placebo) and clinical trial time T, a random effect for subjects, and a treatment by clinical trial time interaction (C\*T). The model will provide least-square mean estimates of difference scores at each session for each treatment. Between treatment outcome contrasts will be performed at Baseline, as a measure of the equivalence of the groups, and at T6 and for the difference between T6 and Baseline. For parameter estimation, the form of the covariance matrix will follow the procedures described for the analysis of Aim 1. Secondary outcome measures will be Negative Emotion, and Psychophysiological arousal. These outcomes will be analyzed in a similar manner to the primary outcome, alcohol craving.

For Hypothesis 3b: Mechanism, AUD and PTSD related measures and cognition (craving, self-efficacy, anxiety, cognitive measures) will be analyzed in the same way as the primary outcome for alcohol use. The primary contrast is change from baseline (B1) at week 6 (T8).

For Hypothesis 3c: Mechanism, anandamide, within- and between-group comparisons of plasma anandamide levels will be assessed following 45 minutes (T1), 1 day (T2), 1 week (T3), 2 weeks (T4), 4 weeks (T6), 6 weeks (T8) of treatment with CBD vs. placebo, and one week (T9) after the completion of treatment. Effects of dose will be assessed and the interaction between group and time- point will be evaluated.

For Hypothesis 4, plasma CBD and THC levels will be analyzed in the same manner as anandamide in Hypothesis 3c.

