Reference Therapy	Placebo with medication management
Key Procedures	Blood draws

	The primary outcome measure for AUD, the number of drinks per day, is the change from baseline to treatment end (week 6, T8), as analyzed with a Mixed Model Repeated Measures (MMRM) with within and between group comparisons. The primary outcome measure for PTSD, PCL-5 total score, and secondary outcomes for traumatic stress induced craving from the human laboratory task, and AUD and PTSD related domains will be analyzed in the same manner.
Statistical Analysis	For secondary outcomes of plasma levels within- and between-group comparisons of plasma CBD levels will be assessed at baseline (pre-CBD levels), following 45 minutes (T1- 45min post-CBD levels), 1 day (T2- 45min post-CBD levels), 1 week (T3- 45min post-CBD and pre-CBD levels), 2 weeks (T4- 45min post-CBD and pre-CBD levels), 4 weeks (T6- 45min post-CBD and pre-CBD levels), 6 weeks (T8- 45min post-CBD and pre-CBD levels), and 7 weeks (T9- pre-CBD levels) after the first CBD vs. placebo dose. Effects of dose will be assessed and the interaction between group and time-points will be evaluated.

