The proposed study is a double-blind, randomized proof-of-concept study designed to assess feasibility and contrast effects of CBD treatment to those of placebo on safety, drinking-related outcomes and PTSD/subthreshold PTSD related outcomes in patients with AUD+PTSD/subthreshold PTSD. We will evaluate the safety of an extended daily CBD treatment regimen in an AUD+PTSD/subthreshold PTSD population and measure resulting CBD, THC, and anandamide levels. We will also generate preliminary data on the impact of CBD on alcohol use, PTSD symptoms, a human laboratory traumatic stress induced craving task, neuropsychological and neurophysiological domains implicated in AUD and PTSD/subthreshold PTSD, and cognitive ability. Cannabidiol levels will be obtained from CBD-treated participants to estimate the plasma levels corresponding with putative therapeutic effects and to determine whether dose accumulation occurs. THC levels will be obtained from CBD-treated participants to determine whether CBD metabolites are converted into THC, as has been suggested in the literature [77]. Anandamide levels will be obtained from all participants to test whether CBD elevates plasma anandamide, and to provide preliminary data for relating anandamide levels to putative therapeutic effects. Following screening and baseline assessments, 48 participants will be randomized in a 5:3 ratio to receive either 600mg CBD/day (PO) or placebo respectively for 6 weeks (N=30 participants on CBD and N=18 participants on placebo). Safety measures (adverse events, cognitive and motoric function), drinking related outcomes and PTSD symptoms will be assessed weekly throughout the study. Human laboratory tasks, neuropsychological domains implicated in AUD and PTSD/subthreshold PTSD and cognition will be assessed at baseline and at the end of treatment. Measurement of circulating levels of Delta-9 THC, 11-Hydroxy Delta-9 THC and Delta-9 Carboxy THC will be obtained from CBD-treated participants only at baseline, 45 minutes, 1 day, 1 week, 2 weeks, 4 weeks, 6 weeks, and 7 weeks after treatment with the first dose of CBD vs. placebo. Anandamide levels will be obtained from both CBD- and placebo-treated participants at the aforementioned timepoints.

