# 4 Study Design and Endpoints

# 4.1 Description of Study Design

The proposed study is a phase I/II, single-center, double-blind, randomized proof-of-concept study designed to assess safety and feasibility in the AUD+PTSD/subthreshold PTSD population and contrast effects of CBD treatment to those of placebo on drinking-related outcomes and PTSD symptoms. We will evaluate the safety of an extended daily CBD treatment regimen in an AUD+PTSD/subthreshold PTSD population, measure resulting plasma and CBD and THC levels, generate preliminary data on the impact of CBD on alcohol consumption and PTSD symptoms, assess the effect of CBD on a human laboratory measure of traumatic-stress induced craving and neuropsychological measures relevant to AUD and PTSD/subthreshold PTSD, and assess the effect of CBD dosing no plasma anandamide levels.

150 participants are expected to be enrolled in the study prior to screening and randomization. Following screening and baseline assessments, 48 participants who fully meet study criteria are expected to be randomized in a 5:3 ratio to receive either 600mg CBD/day (PO) or placebo respectively for 6 weeks (N=30 participants on CBD and N=18 participants on placebo). This dose was selected to optimize anxiolytic affects to target stress induced alcohol craving. Assessments of drinking and PTSD related outcomes will be completed at baseline and weekly over 6 weeks of treatment, with an assessment one week following the end of treatment. The human laboratory task and assessments of cognitive function will be completed at baseline and at the end of 6 weeks of treatment. Measurement of circulating levels of CBD, THC, and THC metabolites (Delta-9 THC, 11-Hydroxy Delta-9 THC and Delta-9 Carboxy THC) will be obtained from CBD-treated participants at baseline, 45 minutes, 1 day, 1 week, 2 weeks, 4 weeks, 6 weeks, and 7 weeks after treatment with the first dose of CBD vs. placebo. Anandamide levels will be obtained from both CBD- and placebo-treated participants at the aforementioned time-points.

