## 20.2 Statistical Hypotheses

Hypothesis 1a Safety and tolerability: CBD will be safe and well tolerated and will not lead to increased plasma THC. No clinically significant cognitive or motoric impairments, CBD-related serious adverse events, persisting adverse effects or treatment associated increases in plasma THC will be observed.

Hypothesis 1b: Alcohol use. Relative to the placebo-treated group, CBD-treated participants will have fewer drinks per day during the 6 weeks of treatment with CBD vs placebo.

Hypothesis 2: PTSD symptoms. Relative to the placebo-treated group, CBD-treated participants will lower PTSD symptoms during the 6 weeks of treatment with CBD vsplacebo.

Hypothesis 3a: Mechanism, traumatic stress-induced craving: Relative to placebo, CBD will be associated with a greater reduction between baseline and end of treatment in trauma induced alcohol craving, negative emotion, and psychophysiological arousal in response to the task.

Hypothesis 3b: Mechanism, AUD and PTSD related measures and cognition: Relative to placebo, CBD will improve self-report measures of craving, anxiety, mood, self-efficacy and cognitive performance.

Hypothesis 3c: Mechanism, anandamide: Relative to placebo, CBD will be associated with a greater increase

Hypothesis 4: CBD plasma levels. Within-group plasma CBD levels will stabilize within one week, i.e. 45 minutes post-CBD dosing levels obtained after 1 week of treatment will not differ from those obtained after 4 weeks of treatment at each dose.

Exploratory Hypothesis 1: Relationship between effects on PTSD symptoms and alcohol use. The onset of reduction in PTSD symptoms will precede the onset of reduction in alcohol use.

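### Section 20.3.3 scores the trauma-craving task at Baseline and T8 but contrasts arms at Baseline and T6, and the measure-specific schedule gives neither the task nor the cognitive battery a pre-dose session

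*Combined protocol and SAP*

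**What the plan says.** **Task, analysis text.** Section 20.3.3 builds a craving score (trauma minus neutral, post minus pre) and says "This difference measure of alcohol craving will be calculated at Baseline, and at week 6 of the clinical trial (T8"). The same paragraph continues: "Between treatment outcome contrasts will be performed at Baseline, as a measure of the equivalence of the groups, and at T6". A third contrast is then added to these two: "and for the difference between T6 and Baseline". The model has treatment, trial time and their interaction. Negative emotion and psychophysiological arousal are to be analysed similarly.

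**Task, hypothesis and design text.** Hypothesis 3a (section 20.2) predicts that "CBD will be associated with a greater reduction between baseline and end of treatment in trauma induced alcohol craving". Section 4.1 says "The human laboratory task and assessments of cognitive function will be completed at baseline and at the end of 6 weeks of treatment", and section 2.3 says "Human laboratory tasks, neuropsychological domains implicated in AUD and PTSD/subthreshold PTSD and cognition will be assessed at baseline and at the end of treatment". The Statistical Analysis row of the Protocol Summary puts "secondary outcomes for traumatic stress induced craving from the human laboratory task", together with AUD and PTSD related domains, under the same approach as the primary outcome, which is a change from baseline to T8.

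**Task, measure-specific text.** The task descriptions in sections 4.2.2 and 7.1.8 give one session, at T6 after 4 weeks of treatment. The T6 list (7.3.3.4) is the only visit list that administers the task. The B1 list (7.3.2) collects imagery scripts, and the T8 list (7.3.3.6) does not mention the task.

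**Cognition.** For hypothesis 3b, which includes the cognitive measures, section 20.3.3 says "The primary contrast is change from baseline (B1) at week 6 (T8"), using the primary model; section 20.3.2 gives that model a baseline covariate. Sections 4.2.2 and 7.1.5 and the T2 and T8 lists time the battery at T2 and T8. Sections 2.3 and 4.1 promise a baseline assessment.

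**The concern.** The contradiction inside section 20.3.3 must be resolved whichever schedule is intended: a score calculated at week 6 cannot feed a contrast at week 4. The larger question is whether a pre-dose score exists. If the task is run only at T6, the baseline equivalence check, the change contrast and the claim in hypothesis 3a have no data behind them. If the cognitive battery is first given at T2, neither the planned change nor the baseline covariate can be formed, and the plan does not say what replaces them.

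The formal SAP promised in section 20.1 can correct contrasts, but it cannot recover a session that was never run. Leaving the visit and contrast open would also let them be settled after the data are seen.

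**Working it through.** The plan gives no figure on this point to reproduce. The check covers timing, estimability and precision.

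**1. Visits.** T6 is week 4 and T8 is week 6 (section 7.3). The first dose is given at B1 (7.3.2). T2 is 1 day after B1 with a window of +5 days, so it falls 1 to 6 days after the first dose and is post-dose. Baseline in 20.3.3 cannot mean the pre-imagery period, because the pre/post difference is already inside the score and the time factor is trial time.

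**2. Estimability for the task.** Take the fixed effects in 20.3.3: intercept, treatment C, time T (0 = Baseline, 1 = follow-up) and C×T. With scores at T6 only, T = 1 on every row, so the T column equals the intercept and the C×T column equals C. The design has rank 2 of 4. The sum C + C×T, which is the T6 contrast, is estimable; C alone (Baseline contrast) and C×T alone (change contrast) are not. One score per person also leaves the subject random effect inseparable from residual error.

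| Task given at | Baseline contrast | T6 contrast | T6 minus Baseline | T8 contrast | T8 minus Baseline |
|---|---|---|---|---|---|
| T6 only (4.2.2, 7.1.8, T6 list) | no | yes | no | no | no |
| Baseline and T8 (4.1; calculation sentence of 20.3.3) | yes | no | no | yes | yes |
| Baseline and T6 (contrast sentence of 20.3.3) | yes | yes | yes | no | no |

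Only the third row supports all three contrasts named in 20.3.3, and it conflicts with the calculation sentence in the same paragraph.

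**3. Precision of the T6 contrast.** Inputs: 30 v 18 (section 20.5.1), two-sided 95% intervals (20.3.1), complete data, outcome in SD units.
- SE = sqrt(1/30 + 1/18) = 0.298 SD
- t(46) = 2.013
- half-width = 2.013 × 0.298 = 0.600 SD

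**4. What a baseline would give.** Let r be the baseline to follow-up correlation, which the documents do not state, and assume equal SDs.
- Unadjusted change: 0.600 × sqrt(2(1 − r))
- Baseline as covariate: about 0.600 × sqrt(1 − r²)

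| Assumed r | T6 alone | Unadjusted change | Baseline-adjusted |
|---|---|---|---|
| 0.3 | 0.60 | 0.71 | 0.57 |
| 0.5 | 0.60 | 0.60 | 0.52 |
| 0.7 | 0.60 | 0.46 | 0.43 |

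**5. Cognition.** Under sections 4.2.2 and 7.1.5 there are two occasions, T2 and T8, both post-dose. The planned contrast and covariate need B1, which neither section includes. The screening, re-screen and B1 lists do not name the battery.

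**The case against.** **Silence in a visit list is weak evidence.** The C-SSRS is required at every study visit (sections 4.2.2 and 7.1.3), yet no list from screening to the week 9 call names it. Sections 2.3 and 4.1 expressly state a baseline for both the task and cognition. The B1 list has a general entry for AUD and PTSD related domains, and section 3.2 speaks of psychological and cognitive domains. A reader might infer that baselines are certainly not being collected; the documents do not prove that. What stands is an unresolved conflict, because sections 4.2.2, 7.1.5 and 7.1.8 give explicit times that exclude B1.

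**T6 in the contrast sentence may be a slip for week 6.** If so, there are two competing task schedules and not three. The sentence still needs correcting, and the conflict with the T6-only text remains.

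**Precision.** From the unadjusted change column alone, a reader might infer that a missing baseline costs precision only when r exceeds 0.5. That does not follow, since the plan's own primary model uses baseline as a covariate (20.3.2). On that use, a missing baseline costs precision at any non-zero correlation.

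**These are secondary outcomes in a pilot, and a SAP is still to come.** Both are true, and they limit the severity. The SAP could settle the T6/T8 conflict but not supply a missing session.

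**The plan for cognition is not confined to 20.3.3.** The Protocol Summary, through its wording on domains, arguably plans the same change, so it needs reconciling too.

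**Conclusion.** The point holds, and it should be fixed before unblinding. Section 20.3.3 cannot be carried out as written under any single schedule. If the measure-specific text governs, 1 of its 3 named task contrasts is estimable (T6 between arms). The Baseline and change contrasts, the time and treatment-by-time terms, the T8 score and hypothesis 3a as worded are not; negative emotion and arousal are affected in the same way. For cognition, the planned change from B1 conflicts with a battery timed at T2 and T8.

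In size, the T6 contrast carries a half-width of 0.60 SD, against about 0.57, 0.52 or 0.43 SD with a baseline covariate at r = 0.3, 0.5 or 0.7. The within-person change claim is lost altogether. These figures assume 30 v 18, complete data, equal SDs and the stated correlations.

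A reader might infer that the task and cognitive results would be invalid, or that the primary results are at risk. Neither is supported. The randomised comparisons at T6 (task) and at T2 and T8 (cognition) remain valid. Drinks per day, PCL-5, PACS, AASE, BAI and BDI-II all have scheduled pre-dose values.

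**What to change.** Before unblinding, state one schedule and make the following agree: the Protocol Summary, sections 2.3, 4.1, 4.2.2, 7.1.5 and 7.1.8, the B1, T6 and T8 lists, hypothesis 3a and section 20.3.3. The documents do not show which schedule is intended, so the sponsor must say.

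**If the task is at T6 only and cognition at T2 and T8:**
- compare arms on the within-session craving score at T6 with a linear model, and treat negative emotion and arousal the same way;
- delete the Baseline, T8 and change contrasts and the time terms from the task analysis;
- reword hypothesis 3a as a between-arm difference at week 4;
- compare cognition between arms at T2 and at T8, and state that T2 is post-dose and not a baseline.

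This adds no procedures. It changes protocol text, however, so it needs an amendment with IRB approval (section 23.2). It gives up the change claim.

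**If a baseline is intended, or is already being collected:**
- list the task and the battery at B1 before the first dose;
- use one follow-up visit (T6 or T8) in the calculation sentence, the contrasts, hypothesis 3a and the visit lists;
- use the baseline as a covariate;
- state how participants without a baseline are analysed.

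This also needs an amendment. Where the baseline task is not already being run, it adds a 120-minute session (the length given in 4.2.2 and 7.1.8). Because B1 currently collects the scripts and gives the first dose, the order of scripts, task and dose must be stated. It cannot supply a baseline for anyone already dosed without one.
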